6.3 Dose modifications

6.3.1 Dose modification and dose delay

For patients who do not tolerate the protocol-specified dosing schedule, dose interruptions and/or reductions are either recommended or mandated in order to allow patients to continue the study treatment. These dose changes must be recorded on the Dosage Administration Record CRF.

6.3.1.1 Dose modification for hematologic toxicity

For all patients who receive ruxolitinib, there are mandatory dose decreases or dose interruptions for declining platelet counts, hemoglobin or ANC levels that might be observed while on ruxolitinib therapy. Deviations to mandatory dose interruptions and/or reductions are not allowed.

Doses may be titrated based on safety. Dosing must be held if platelet counts decline below 25,000/ μ L or if ANC that is \leq 500/ μ L or Hemoglobin is \leq 6.5 g/dL despite transfusions, while receiving ruxolitinib.

After dose interruption, when blood counts recover, dosing must be restarted at 5 mg twice daily and gradually increased based on careful monitoring of blood cell counts.

Table 6-2 Dose modifications for hematologic toxicity

[figure not shown]
The instructions provided in this table and the criteria for dose reduction / interruption are used to determine a protocol deviation.

Hematology Value at time of decline:	Dose at the time of decline				
	25 mg BID	20 mg BID	15 mg BID	10 mg BID	5 mg BID
	Dose reduction to				
Platelet < 125,000 / μ L	20 mg BID	20 mg BID	15 mg BID	10 mg BID	5 mg BID
Platelet < 100,000 / μ L	15 mg BID	15 mg BID	15 mg BID	10 mg BID	5 mg BID
Platelet < 75,000 / μ L	10 mg BID	10 mg BID	10 mg BID	10 mg BID	5 mg BID
Platelet < 50,000 / μ L	5 mg BID	5 mg BID	5 mg BID	5 mg BID	5 mg BID
Platelet < 25,000 / μ L	Treatment must be interrupted.				
Hemoglobin \leq 6.5 g/dL despite transfusions	Treatment must be interrupted.				
Absolute neutrophil count < 0.5 x 10 ⁹ /L	Treatment must be interrupted.				

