6.1.1 Dosing regimen

Table 6-1 Dose and treatment schedule

Study treatments	Pharmaceutical form and route of administration	Dose	Frequency and/or Regimen
INC424/ruxolitinib	5mg Tablet for oral use	Starting dose 10 mg bid (2 tablets of INC424 5mg, approximately 12 hours apart: morning and night), to be increased or decreased per standardized dosing paradigm and not to exceed 25 mg bid.	Twice Daily (BID), unless instructed to temporarily withhold dosing for safety

INC424 (ruxolitinib) 10 mg BID (2 tablets of INC424 5mg) will be self-administered as starting dose for treatment of anemic MF patients. This dose will be maintained for the first 12 weeks and titrated up thereafter unless they have met criteria for dose hold or dose reduction.

Ruxolitinib should be taken orally, approximately 12 hours apart (morning and night) without regards to food. Ruxolitinib will be self-administered by the patient in an outpatient setting, and each investigator should instruct the patient to take the study drug as per protocol. All dosages prescribed and dispensed to the patient and all dose changes during the study must be recorded on the appropriate case report form (CRF).

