6.3.5 Restarting or reinstating previous dose

Dosing of ruxolitinib may be restarted or increased following recovery of platelet counts and/or ANC to acceptable levels as illustrated in [Table 6-3](#). The objective for restarting or

escalating after a reduction for safety is to find the highest safe dose of ruxolitinib for each patient, with increases in dose generally not more than in increments of 5 mg BID and not more often than every 2 weeks. Similarly, ANC levels that decline to < 500/ μ L necessitate immediate dose interruption ([Section 6.3.1.1](#)). ANC level recovery to 500 / μ L and above but less than 750/ μ L will allow dosing to be restarted at 5 mg BID, and ANC levels between 750/ μ L, but < 1000/ μ L may restart at 10 mg BID. Absolute neutrophil count level increases to above 1000/ μ L will allow a further dose increase.

[figure not shown]
After restarting using the guidelines in [Table 6-3](#), if it is found that a patient cannot tolerate the lowest allowed dose (5mg BID, or 5mg QD with concomitant CYP3A4 inhibitor, see [Section 6.4.2](#)) without platelets falling below 25,000/ μ L, neutrophils falling below 500/ μ L, or Hgb falling below 6.5g/dL despite the use of transfusion therapy, drug must be permanently discontinued ([Section 6.3.1.1](#)).

Table 6-3 Restarting or reinstating previous ruxolitinib dose after safety interruptions or dose reductions

Current Platelet Count after interruption or reduction	Maximum Dose for Restarting or reinstating previous dose after interruption or reduction
< 25,000/ μ L	Continue hold
25,000/ μ L to < 50,000/ μ L	5 mg BID
50,000/ μ L to < 75,000/ μ L	10 mg BID
75,000/ μ L to < 125,000/ μ L	15 mg BID
\geq 125,000/ μ L	20 mg BID
Current ANC Level after interruption or reduction	Dose Restart or Dose Increase Guidelines
< 500/ μ L	Continue hold
500 to < 750/ μ L	5 mg BID for at least 2 weeks; if stable, may increase to 10 mg BID
750 to < 1000/ μ L	10 mg BID for at least 2 weeks; if stable, may increase to 15 mg BID
1000 to < 1500/ μ L	15 mg BID for at least 2 weeks; if stable may increase to 20 mg BID
\geq 1500/ μ L	20 mg BID
NOTE: Whether the dose interruption occurred because of neutropenia, thrombocytopenia or both, when restarting, both the platelet count and ANC must be considered to determine the restart dose, with the lower calculated dose being used.	

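### After a platelet or neutrophil hold, Section 6.3.1.1 requires a 5 mg BID restart while Section 6.3.5 and Table 6-3 allow a higher one, and nothing says which prevails

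*Protocol*

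**What the plan says.** Protocol Section 6.3.1.1 sets the mandatory holds for low platelets, ANC or hemoglobin. It then gives one restart instruction, whatever the recovered count: "dosing must be restarted at 5 mg twice daily and gradually increased based on careful monitoring of blood cell counts".

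Section 6.3.5 covers restarting after the same holds. It cites 6.3.1.1 for the rule that ANC below 500/µL must "necessitate immediate dose interruption". It then sets restart doses by recovered ANC: 5 mg BID at 500 to <750/µL, while a patient at 750 to <1000/µL "may restart at 10 mg BID". Its next paragraph opens "After restarting using the guidelines in" Table 6-3. That table is titled "Restarting or reinstating previous ruxolitinib dose after safety interruptions or dose reductions" and runs up to 20 mg BID for both platelets and ANC. Its note applies "Whether the dose interruption occurred because of neutropenia, thrombocytopenia or both" and says that "both the platelet count and ANC must be considered to determine the restart dose, with the lower calculated dose being used".

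Section 6.3.3 refers the reader to 6.3.6 for reinstatement after a hold. Section 6.3.6 concerns overdose and contains no restart rule.

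**The concern.** The two sections give different restart doses for the same event. One is worded as an obligation and the other as a count-based allowance. The only tie-break, in the Table 6-3 note, ranks platelets against ANC; it does not rank Table 6-3 against 6.3.1.1.

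Two sites with the same counts in front of them could restart the same patient at different doses. The patient has just had a mandatory hold, and the protocol's own safety summary (Section 1.2.1.2.3) describes anemia, thrombocytopenia and neutropenia on this drug as dose related. Section 12 permits no authorized deviations, so a site needs a single rule to follow. Whether a restart above 5 mg BID would count as a deviation is not settled either: the deviation sentence in 6.3.1.1 refers to Table 6-2 and the reduction and interruption criteria, which set no restart dose.

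**Working it through.** There is no plan figure to reproduce. The check sets the two rules side by side and counts where they differ.

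**Inputs**

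- Section 6.3.1.1: restart at 5 mg BID at any recovered count.
- Table 6-3, platelets per µL: 25,000 to <50,000 gives 5 mg BID; 50,000 to <75,000 gives 10; 75,000 to <125,000 gives 15; ≥125,000 gives 20. These are maxima.
- Table 6-3, ANC per µL: 500 to <750 gives 5 mg BID; 750 to <1000 gives 10; 1000 to <1500 gives 15; ≥1500 gives 20.
- Section 6.1.1: the starting dose is 10 mg BID and "This dose will be maintained for the first 12 weeks and titrated up thereafter". So 10 mg BID is the highest dose in use before week 12. Section 6.2.3 allows 15 mg BID from week 12, 20 from week 16 and 25 from week 20.
- Section 6.3.5: increases are generally at most 5 mg BID, no more often than every 2 weeks.

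**Assumption.** A restart does not exceed the dose before the hold. The Table 6-3 title suggests this but no text states it.

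**Dose under Section 6.3.5** = min(platelet dose, ANC dose, prior dose), over the 4 × 4 = 16 combinations in which neither count requires a continued hold:

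| Prior dose | 5 mg BID | 10 mg BID | 15 mg BID | 20 mg BID | Cells above 5 mg BID |
|---|---|---|---|---|---|
| 5 mg BID | 16 | 0 | 0 | 0 | 0 |
| 10 mg BID | 7 | 9 | 0 | 0 | 9 |
| 15 mg BID | 7 | 5 | 4 | 0 | 9 |
| 20 or 25 mg BID | 7 | 5 | 3 | 1 | 9 |

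The 7 cells at 5 mg BID are those with either count in its first recovery band: 4 + 4 − 1 = 7. There the rules agree. The other 16 − 7 = 9 cells need platelets ≥50,000/µL and ANC ≥750/µL. These are table cells, not patient frequencies.

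**When the conflict arises.** A recovering count passes first through a band where both rules give 5 mg BID. The conflict therefore needs a count that crosses that band between checks, or a delayed restart, which Section 6.3.3 permits for up to 8 weeks. Example: a week 8 patient on 10 mg BID is held for ANC below 500/µL, and the next result is ANC 800/µL with platelets 150,000/µL. Section 6.3.1.1 gives 5 mg BID; Section 6.3.5 allows 10.

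**Size before week 12.** 10 versus 5 mg BID is 20 − 10 = 10 mg/day. Over one usual two-week step, 10 × 14 = 140 mg.

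**Time to regain the earlier dose from 5 mg BID** = (target − 5)/5 × 2 weeks: 2 weeks for 10 mg BID, 4 for 15 and 6 for 20, at the usual step.

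**Hemoglobin holds.** There is no conflict. Table 6-3 has no hemoglobin row and its note names only neutropenia and thrombocytopenia.

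**The case against.** The strongest reply has four parts.

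- **The platelet column is a ceiling.** A 5 mg BID restart satisfies both rules. That is correct, but a site using the ceiling would be doing what 6.3.1.1 forbids. All 9 conflicting cells also have ANC ≥750/µL, where the ANC rows name 10 mg BID or more.
- **Monitoring narrows the trigger.** Section 6.3.3 recommends counts at least twice weekly when platelets are below 50,000/µL or ANC below 500/µL, so skipping the agreement band is less likely. This stands, but it does not remove delayed restarts. Section 6.4.2 also allows granulocyte growth factors during a hold, which could plausibly carry ANC past the band. And Table 6-2 has no ANC reduction step, so a neutropenia hold can come directly from 10 mg BID or above.
- **The disputed doses are not out of line with the rest of the protocol.** At each platelet level the Table 6-3 maximum is no higher than the dose Table 6-2 lets a patient keep, and 10 mg BID is the study's own starting dose. This is fair and limits the safety argument, as does the absence of any cited comparison of cytopenia at 5 and 10 mg BID. It does not tell a site which rule to follow.
- **A 5 mg BID restart has a price.** Regaining 10 to 20 mg BID takes about 2 to 6 weeks at the usual step, possibly before the week 24 spleen assessment. That is a genuine, small downside, but the existing mandatory wording already imposes it. Section 6.3.5 states its aim as reaching each patient's highest safe dose, so the alternative resolution is also defensible.

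**Conclusion.** The contradiction is real and should be fixed. It applies to platelet and ANC holds only, and only when platelets are ≥50,000/µL and ANC ≥750/µL at restart. Before week 12 it amounts to 10 versus 5 mg BID; in patients already titrated up, 10, 15 or 20 versus 5 mg BID. The breakdown by prior dose rests on the assumption that a restart does not exceed the earlier dose.

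The consequence is inconsistent restart dosing. The primary analysis rules do not depend on it, and the exclusions in SAP Section 2.2.3 contain no dose-modification item. The documents give no frequency of holds on a 10 mg BID start, so the number of patients affected cannot be estimated.

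**What to change.** Keep one restart rule. The preferred option is 5 mg BID after any hematologic hold, hemoglobin included: it is the cautious choice, it already stands in 6.3.1.1, and it is the restart dose in the label appended as Appendix 6 (SmPC section 4.2). Then amend Section 6.3.5:

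1. In the ANC text, let 750 to <1000/µL permit an increase up to 10 mg BID after a 5 mg BID restart, instead of a 10 mg BID restart.
2. Reword the Table 6-3 title and both column headings so that the doses are maxima for increases after that restart, or for reinstatement after a reduction.
3. In the note, make the lower of the platelet and ANC doses the ceiling for increases, not the restart dose.
4. In the paragraph before the table, refer to 6.3.1.1 for the restart dose.

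The alternative is one change in 6.3.1.1: defer to Table 6-3 for platelet and ANC holds and keep 5 mg BID for hemoglobin holds. It touches less text and avoids slower re-escalation.

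Either way, correct the Section 6.3.3 pointer from 6.3.6 to 6.3.5. As an editorial matter, use one inequality for hemoglobin 6.5 g/dL and one for ANC 500/µL throughout 6.2.3, 6.3.1.1, Table 6-2, 6.3.3 and Table 6-3.

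The cost is amendment text and a site letter. The sample size and analysis methods do not change.

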6.3.1.2 Dose modification for renal impairment

No specific dose adjustment is needed in patients with mild or moderate renal impairment.

Patients diagnosed with severe renal impairment while receiving ruxolitinib should be carefully monitored and need to have their doses reduced to avoid adverse drug reactions (ADRs).

6.3.1.3 Dose modification for hepatic impairment

Patients diagnosed with hepatic impairment while receiving ruxolitinib should be carefully monitored and may need to have their dose reduced to avoid adverse drug reactions.

Patients diagnosed with hepatic impairment while receiving ruxolitinib should have complete blood counts, including a white blood cell count differential (neutrophils, lymphocytes, eosinophils, basophils, monocytes, and blast cells), monitored at least every one to two weeks for the first 6 weeks after initiation of therapy with ruxolitinib and as clinically indicated thereafter once their liver function and blood counts have been stabilized. ruxolitinib dose can be titrated to reduce the risk of cytopenia.

6.3.1.4 Dose reduction for non-hematological safety

Although study guidelines provide for dose reduction/interruption for the management of hematologic or non-hematologic toxicities that occur during the course of the study, the investigator should determine whether permanent discontinuation of study drug is necessary.

[figure not shown]
6.3.2 Optional dose tapering strategy in the event of study drug discontinuation

Following interruption or discontinuation of ruxolitinib, symptoms of myelofibrosis may return over a period of approximately one week. There have been cases of patients discontinuing ruxolitinib who sustained more severe events, particularly in the presence of acute intercurrent illness. It has not been established whether abrupt discontinuation of ruxolitinib contributed to these events. Unless abrupt discontinuation is required, gradual tapering of the dose of ruxolitinib may be considered, although the utility of the tapering is unproven.

When a decision is made to permanently discontinue ruxolitinib therapy for reasons other than low platelet counts or ANC levels, a dose tapering strategy may be considered, based on evaluation of the condition of the patient, current dosing regimen, and the clinical judgment of the investigator. If considered to be medically necessary, the investigator may use any treatment to manage withdrawal from ruxolitinib including a gradual tapering of the study drug dosage or use of other medications to manage adverse drug reactions of discontinuation. Short-term courses of corticosteroids have been used to moderate the withdrawal of ruxolitinib and may be considered as part of a tapering strategy. Corticosteroids may be started prior to, or concurrent with, ruxolitinib tapering. When a decision has been made to discontinue the patient with utilization of a tapering strategy, regardless of the use of concomitant medications, safety data will continue to be assessed in accordance with the protocol until the end of ruxolitinib administration and in the event of an AE through resolution of the AE.

6.3.3 Dose interruption and discontinuation of study drug

In some circumstances, it may be necessary to temporarily interrupt treatment as a result of adverse drug reaction that may have an unclear relationship to study drug. Except in cases of emergency or for protocol mandated holds for ANC, hemoglobin or platelet count, it is

recommended that the investigator consult with the Sponsor medical monitor (or other representative of the Sponsor) before temporarily interrupting therapy.

Study drug may be held by the investigator at any time if there is concern about patient safety, and for all aspects of the conduct of the protocol the safety of the individual patient is paramount. Treating investigators may employ any means necessary to ensure patient safety, particularly in medical circumstances not anticipated by this protocol. Dosing must be halted immediately if any of the following occur:

- Platelet counts fall below 25,000/ μ L
- ANC levels fall below 500/ μ L
- Hemoglobin cannot be maintained ≥ 6.5 g/dL despite the use of transfusion therapy

Dosing may be reinstated following dose holding as detailed in [Section 6.3.6](#). In order to provide sufficient data to make the dose adjustment decisions, it is recommended that hematology parameters be obtained at least weekly for platelet count $< 100,000/\mu$ L or ANC $< 1000/\mu$ L and at least two times weekly for platelet count $< 50,000/\mu$ L or ANC $< 500/\mu$ L. (Note: patients with platelet counts of $< 10,000/\mu$ L should be hospitalized, unless local or national practice does not permit it).

If a patient on a dose-hold requires frequent testing for safety parameters, these tests may be performed at a local laboratory. If the study drug is interrupted for any reason for more than 8 weeks, dosing may not be restarted, except in the case of splenectomy, for which a maximum 12 week period of study drug interruption is permitted. Although study guidelines provide for dose reduction/interruption for the management of hematologic or non-hematologic toxicities that occur during the course of the study, the following guidelines should be used to determine whether permanent discontinuation of study drug is necessary.

6.3.4 Discontinuation of study drug for hematologic toxicity:

Study drug MUST be permanently discontinued if the lowest allowed dose (5 mg BID or 5 mg QD with concomitant CYP3A4 inhibitor) is not tolerated due to the following:

- Platelets cannot be maintained $\geq 25,000/\mu$ L.
- Absolute neutrophil count cannot be maintained $\geq 500/\mu$ L.
- Hemoglobin cannot be maintained ≥ 6.5 g/dL despite the use of transfusion therapy.

In the event that any patient permanently discontinues the study drug, regardless of reason, reasonable efforts should be made to have the patient return for an early termination visit and have the End of Treatment evaluations and Safety Follow up evaluations completed.

The date the patient discontinued the study drug and the specific reason for discontinuation will be recorded in the eCRF. This will include reasons such as discontinued due to disease worsening or withdrawn due to adverse event. This information will be used to summarize the reasons for study withdrawal.

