2.2 Rationale for the study design

The COMFORT studies compared the effects of ruxolitinib with placebo or best available therapy, respectively and showed that ruxolitinib treatment significantly reduced splenomegaly and provided marked improvements in MF-related symptoms and quality-of-life (QOL) measures compared with controls, regardless of JAK2V617F mutational status. The clinical benefit and safety of ruxolitinib treatment in COMFORT -I and COMFORT-II have been maintained with subsequent longer-term follow-up. As anticipated, the effect of JAK2 inhibition on hematopoiesis resulted in dose-dependent anemia and thrombocytopenia. The majority of these cytopenias occurred in the first 8 to 12 weeks of treatment, and they were generally manageable with dose reductions and/or red blood cell transfusions.

There is increasing literature suggesting the use of a 10 mg BID starting dose with subsequent up titrations depending on safety and efficacy in patients with anemia at the time of treatment initiation with ruxolitinib (Tabarrokhi 2013, Cervantes 2014, Reilly 2014, Harrison 2013, Ho 2015). This dosing approach for anemic MF patients will be systematically studied in this prospective multicenter phase II open label single arm trial to determine if the levels of spleen length reduction and symptom improvement are consistent with those reported in previous clinical trials with ruxolitinib in patients with anemia and doses according to platelet counts at the moment of treatment initiation, and whether this lower starting dose and up titration approach may minimize the initial hemoglobin and platelet declines and transfusion requirements. The efficacy and safety of ruxolitinib with starting doses based on platelet counts in MF patients including those with anemia at baseline have been well studied and characterized in several clinical trials (COMFORT I, COMFORT II, JUMP).

This is an open-label, single-arm study of treatment with ruxolitinib for 48 weeks in patients who presents with transfusion dependent or independent anemia at screening defined as an hemoglobin <10 g/dL.

Ruxolitinib will be self-administered as BID oral treatment. The starting dose is 10 mg BID for all enrolled patients and gradual up titrations will start at week 12 determined by the level of efficacy achieved and the tolerability.

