6.2.3 Guidelines for dose escalations

Dose up titrations will be based on efficacy and platelet counts provided that ANC is $>500 \mu\text{L}$ and Hb level is $\geq 6.5 \text{ g/dL}$ as follows:

- A dose of 15 mg BID should be targeted in patients with platelet count $\geq 100 \times 10^9/\text{L}$ and $\leq 200 \times 10^9/\text{L}$ from week 12. This dose increase is optional for patients that achieved a $\geq 50\%$ reduction in spleen length at this visit relative to Baseline.
- A dose of 20 mg BID should be targeted in patients with platelet count $\geq 200 \times 10^9/\text{L}$ from week 16. This dose increase is optional for patients that achieved a $\geq 50\%$ reduction in spleen length at this visit relative to Baseline.
- Maximum dose allowed in the study is 25 mg BID and may be used from Week 20 in patients that did not achieve a 50% reduction in spleen length relative to Baseline and provided that platelet count is $\geq 200 \times 10^9/\text{L}$ at this visit.
- Patients who did not qualify for a dose increase at Week 12, may qualify for an increase at week 16 (from 10 mg BID to 15 mg BID). In that case, the Week 12 dose increase rules will apply. Similarly, patients who did not qualify for a dose increase at Week 16, may qualify for an increase later (from 15 mg BID to 20 mg BID). In that case, the Week 16 dose increase rules will apply.

Figure 6-1 Dosing Up-titration Diagram

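### After a first dose increase made at a scheduled visit at Week 24 or later, the readable protocol text requires no blood count for 8 to 16 weeks, against 2 to 4 weeks in the appended label

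*Protocol*

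**What the plan says.** **Dose increases (Protocol 6.2.3).** "Dose up titrations will be based on efficacy and platelet counts provided that ANC is" above 500/µL and hemoglobin is at least 6.5 g/dL. The targets are 15 mg BID from Week 12 and 20 mg BID from Week 16. Two provisions reach beyond Week 20. A patient who did not qualify at Week 16 "may qualify for an increase later (from 15 mg BID to 20 mg BID"), and "Maximum dose allowed in the study is 25 mg BID and may be used from Week 20". Neither has an end date. Both 20 and 25 mg BID need platelets of at least 200 x 10^9/L.

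**Scheduled counts (Protocol 4.1, 7.1.3, 7.2.2.7, Table 7-1).** Hematology is drawn at each visit. Visits are 4 weeks apart to Week 24 and 12 weeks apart afterwards, with windows of ±7 days to Week 24 and ±14 days after that.

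**Extra counts (Protocol 6.3.3).** "it is recommended that hematology parameters be obtained at least weekly for platelet count" below 100,000/µL or ANC below 1000/µL, and twice weekly below 50,000/µL or 500/µL. Neither a dose increase nor a hemoglobin value is a trigger.

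**Actions on a count (Protocol 6.3.1.1).** For all treated patients "there are mandatory dose decreases or dose interruptions for declining platelet counts, hemoglobin or ANC levels". In Table 6-2 the first platelet step at 25 mg BID is at below 125,000/µL.

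**Appended label (Protocol Appendix 6).** Label section 4.2 advises a blood count every 2 to 4 weeks until the dose is stable. Label section 4.4 advises closer monitoring when baseline hemoglobin is below 10 g/dL. Inclusion criterion 4 makes that the whole trial population.

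**The concern.** The mandatory reductions and holds protect a patient only when a count is taken. Up to Week 24 an increase is nominally followed by a count at 28 days, which is within the label's interval. From Week 24 the visit spacing triples, yet first increases are still permitted and the readable text ties no count to them. The extra-count rule does not close the gap, because it reacts to a low value that someone must first measure.

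The risk is known to rise with dose. In the phase I/II study summarised in Protocol 1.2.1.2.3, Grade 3 thrombocytopenia occurred in 3% of patients at 15 mg BID and 23% at 25 mg BID; Grade 4 occurred in 0% and 6%. Those are dose cohorts, not patients titrated as here, so the figures give direction rather than an expected rate. For hemoglobin, label section 4.4 reports that 79.3% of patients starting below 10 g/dL fell below 8 g/dL, against 30.1% of the others.

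The protocol does ask for closer counts in other situations: every one to two weeks after hepatic impairment is diagnosed (6.3.1.3), and more often on starting a strong CYP3A4 inhibitor (6.4.2). A deliberate late increase has no matching provision.

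**Working it through.** **1. Visit days.** Visit day = 7 x week number. This gives 7 x 20 = 140, 7 x 24 = 168, 7 x 36 = 252, 7 x 48 = 336, 7 x 60 = 420 and 7 x 72 = 504, all as printed in Table 7-1. For Week 84 the table prints Day 598, whereas 7 x 84 = 588. That looks like a typing slip and is not used here.

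**2. Gap from an increase to the next scheduled count.** The increase is taken to be made at a scheduled visit. Nominal gap = difference in visit days. Shortest and longest gap = nominal minus or plus the sum of the two visit windows.

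| Increase at | Next count | Nominal (days) | Shortest (days) | Longest (days) |
|---|---|---|---|---|
| Week 20 | Week 24 | 168 - 140 = 28 | 28 - (7 + 7) = 14 | 28 + (7 + 7) = 42 |
| Week 24 | Week 36 | 252 - 168 = 84 | 84 - (7 + 14) = 63 | 84 + (7 + 14) = 105 |
| Week 36 | Week 48 | 336 - 252 = 84 | 84 - (14 + 14) = 56 | 84 + (14 + 14) = 112 |

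Increases at Weeks 12 and 16 give the same result as Week 20. Visits after Week 48 are spaced like Week 36 to 48. In weeks, the late gap is 9 to 15 for an increase at Week 24 and 8 to 16 for one at Week 36 or later.

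**3. Against the label's upper limit of 4 weeks (28 days).** 56/28 = 2.0; 63/28 = 2.25; 84/28 = 3.0; 105/28 = 3.75; 112/28 = 4.0.

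**4. Who can have a late first increase.** Assume steps of 5 mg BID made at scheduled visits. The uninterrupted path is 15, 20 and 25 mg BID at Weeks 12, 16 and 20. One missed step puts 25 mg BID at Week 24 at the earliest; two put it at Week 36.

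**5. Whether 6.3.3 fills the gap.**
- *Platelets.* The minimum for 20 or 25 mg BID is 200,000/µL and the trigger is below 100,000/µL, so the trigger cannot be met at the count that permits the increase. Reaching it takes a fall of more than 1 - 100/200 = 50%, which only a further count would show.
- *First mandatory reduction at 25 mg BID.* This is reached by a fall of more than 1 - 125/200 = 37.5%. A patient at, say, 110,000/µL must be reduced but does not meet the extra-count trigger.
- *ANC.* Increases are allowed above 500/µL and the weekly-count trigger is below 1000/µL. A patient raised with ANC between those values is therefore already covered by the recommendation; one with ANC of at least 1000/µL is not.
- *Hemoglobin.* There is no trigger at any level.

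**The case against.** Several parts of the opposing case stand.

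- **Figure 6-1 is not available to us.** Protocol 2.1 sends the reader to that diagram for dosing detail. It could contain a count instruction or a limit on late increases. The finding is therefore about the readable text only.
- **Increases after an interruption or reduction are partly covered.** Under 6.3.1.1 the dose is then "gradually increased based on careful monitoring of blood cell counts", and 6.3.5 sets "increases in dose generally not more than in increments of 5 mg BID and not more often than every 2 weeks". Such increases may also fall between visits, nearer the next scheduled count. The 8-to-16-week range does not apply to them.
- **The default path is not affected.** A patient who misses no step, and is raised when first allowed, is on 4-weekly counts throughout.
- **General safeguards exist.** Protocol 2.2 says "gradual up titrations will start at week 12 determined by the level of efficacy achieved and the tolerability". Protocol 2.6 relies on close monitoring, 6.3.3 leaves investigators free to do whatever safety requires, and SAP 2.1.1 expects unscheduled assessments. Investigators also hold the label.

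The last item narrows the practical risk but fixes no date for a count. A reader might infer that these patients go unobserved for up to 16 weeks. The documents do not support that: unscheduled counts are allowed, adverse events are followed, and the hemoglobin hold presupposes transfusion care. What is missing is a required count, not access to one.

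**Conclusion.** The point holds as a cheap safety improvement, not as an error. When a first increase under 6.2.3 is made at a scheduled visit at Week 24 or later, the readable text requires no count for nominally 84 days (63-105 after Week 24; 56-112 after Week 36 or later). That is 2 to 4 times the label's 4-week limit, in the population for which the label advises closer monitoring. The recommended extra counts do not reach a patient raised with platelets of at least 200 x 10^9/L and ANC of at least 1000/µL.

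This rests on increases being made at scheduled visits and on nothing in Figure 6-1 supplying the count; confidence is moderate for the second reason. How many patients will have a late first increase cannot be derived from the documents.

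A reader might also infer that the efficacy result or the laboratory tables are compromised. The documents do not support this. The success rule depends only on the Week 24 spleen response count, so its stated operating characteristics (0.0301 at a true rate of 15%, 0.9339 at 35%) do not change. For the worst-grade tables in SAP 2.8.3, neither the size nor the direction of any effect of irregular counts can be derived.

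**What to change.** Add one sentence to Protocol 6.2.3, with a cross-reference in 6.3.3:

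*After any dose increase under this section made at Week 24 or later, obtain a local hematology count (hemoglobin, platelets, ANC) within 4 weeks.*

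If Figure 6-1 already carries such an instruction, repeating it in the text is enough. The cost is one extra blood draw per late increase. Protocol 7.2.2.7 already uses the site's own laboratory, so no new arrangement is needed. No change to the SAP is proposed.
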